**Yunnan-ADARC HIV Prevention Program: Developing and
Testing a Model to Implement and Sustain PrEP Delivery in China**

NCT03992274

Principal Investigator: [name], MPP, MSc

Effective: 08/31/2023 (IRB Approved)

Research Aims & Abstracts

B-HAPPY is a multisite randomized stepped-wedge study to compare the effectiveness of two PrEP implementation strategy bundles: 1) Standard Implementation: comprising the strategies that the Yunnan CDC would usually use to introduce HIV prevention innovations in the absence of the proposed study; and 2) Enhanced Implementation: standard implementation enhanced by an approach guided by the Stages of Implementation Completion (SIC) framework to plan and implement PrEP.

We **hypothesize** that adding SIC-guided implementation onto standard health system implementation of PrEP will improve outcomes and lead to greater likelihood of a) implementation success and b) sustainment. **Successful implementation** will be defined as a site achieving Five-80% targets and maintaining them three months in a row: 1) Awareness of PrEP among 80% of MSM clients; 2) PrEP eligibility assessment for 80% of MSM clients; 3) PrEP linkage for 80% of MSM clients who wish to start and are medically-eligible; 4) PrEP initiation for 80% of MSM who linked to PrEP services; and 5) six-month PrEP continuation for 80% of those who remain PrEP-eligible.

Sustainment will be defined as achieving the Five-80s continuously over 6-months.

To examine the implementation process and efficiency of the Enhanced versus Standard implementation approaches we will use SIC and COINS tools to monitor sites for implementation process and resource use. Outcomes will include proportion of implementation activities completed, duration of each implementation phase, and cost and resource allocation for completion of each implementation phase. Based on robust studies that assess implementation using the SIC, we **hypothesize** that time and

resources spent in Pre-Implementation will be associated with higher odds of successful implementation and sustainment

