it will be used as an observational assessment tool only, and Enhanced, when it will be used both to guide implementation and to assess it. During Enhanced Implementation each site will receive Implementation Support to plan and introduce PrEP by following the eight stages of the PrEP-adapted SIC. Implementation Support will involve a centralized TA system developed using US-based PrEP experience. The support will utilize a **SIC-guided systems analysis and improvement approach** that focuses on addressing implementation issues identified through real-time analysis of client, provider/site, and implementation data. During the study, sites will participate in four study periods: a Pre-Baseline Period (Routine service with no PrEP implementation), a Baseline Period (Standard Implementation of PrEP), an Experiment Period (Enhanced Implementation of PrEP), and a Post-Experiment-Sustainment Period. Sites are randomized to the *timing* of the intervention phase—the intervention condition changes over time and the intervention effect is the difference in outcomes between the Baseline and Experiment Periods, and the Post-Experiment and Baseline Periods.

We hypothesize that adding SIC-guided implementation onto standard health system implementation of PrEP will improve outcomes and lead to greater likelihood of a) implementation success and b) sustainment. Successful implementation will be defined as a site achieving "Five-80%" targets and maintaining them three months in a row (Aim 1): 1) *Awareness of PrEP among 80% of MSM clients*; 2) *PrEP eligibility assessment for 80% of MSM clients*; 3) *PrEP linkage for 80% of MSM clients who wish to start and are medically-eligible*; 4) *PrEP initiation for 80% of MSM who are linked to PrEP services*; and 5) *six-month PrEP continuation for 80% of those who remain PrEP-eligible*. Sustainment will be defined as achieving the Five-80% targets continuously

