over 6 months. The study team set 80% targets for two reasons: 1) 80% targets are commonly used in observational facilitated training in implementation processes; 2) the PI's recently-published PrEP modeling analysis clearly showed the differential epidemiological impact a high real-world PrEP effectiveness would have compared to a low real world effectiveness: with 80% effectiveness, PrEP would lead to 345,000 infections averted over a 20-year horizon compared to 219,000 with 50% effectiveness and 87,900 with 20% effectiveness (Zhang et al., 2018), spurring the team to choose ambitious targets that could drive down infections among MSM. To examine the implementation process and efficiency of the Enhanced versus Standard implementation approaches we will use SIC and COINS tools to monitor sites for implementation process and resource use. Outcomes will include proportion of implementation activities completed, duration of each implementation phase, and cost and resource allocation for completion of each implementation phase (Aim 2). Based on robust studies that assess implementation using the SIC, *we hypothesize that time and resources spent in Pre-Implementation will be associated with higher odds of successful implementation and sustainment.*

Recruitment

All recruitment activities will take place at our international site (Yunnan, China) and will be conducted in Mandarin Chinese, the primary language of the region, by Chinese-speaking research staff. All research staff will complete the required human subject training before conducting any recruitment activities. All procedures related to recruitment have been reviewed and approved by Yunnan CDC IRB. Columbia personnel will not be involved in the recruitment of participants.

Two types of participants will be recruited for in-depth interviews in our study: (1) MSM clients of participating facilities; (2) program staff who are involved in PrEP implementation. We will conduct the interviews with clients and program staff in each study period, as a result, a total of four rounds of interviews will be conducted.

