Third, the effective sample size is used in a conventional power analysis. The results indicated that power is .80 to detect an effect of OR = 3.3 for the effect of Standard Implementation on client services outcomes. This is equivalent to a medium-to-large standardized effect of $d=0.66$, or a between-period difference in probability of 29%. For a less conservative nesting effect ($=0.10$), the sample is sufficient to detect OR=2.0, or a 16% between-period difference.

Evaluation of Specific Aim 2: To compare the time, costs, and resources required for Standard versus Enhanced PrEP implementation. The expected opportunity cost of implementation for sites will be modeled using an estimator that will identify the “best practice” implementation costs. The theoretical model assumes that sites attempt to minimize costs of implementation in order to maximize excess revenue subject to a standard economic production function. **This production function supports a dual cost function: where C_{it} represents the SIC-measured implementation costs for the i^{th} program in the t^{th} phase, X_{it} are characteristics of program i in phase t , is an i.i.d. error term, is a one-sided error term corresponding to the technical inefficiency for the i^{th} practice in phase, and represents the coefficients of the best practice (most efficient) cost function. We assume the best-practice cost function is of the CobbDouglas form, such that the log-linear transformation yields.**

With estimates of the model parameters, we will predict the best practice implementation costs and technical inefficiency costs for each program. We will also explore which program characteristics and contextual factors are associated with higher or lower estimated inefficiencies. We will include measures of the “best practice” implementation costs, technical cost inefficiency and intervention costs in a model predicting successful implementation. The aggregated cost variables will be added to linear probability models (because cost measures require a prediction substitution model) as covariates alongside SIC Duration and Proportion scores to predict the binary outcome of whether a program sustained a minimum of 1-year post Stage 8 of the SIC (Competency). Differences in use of resources will be examined between sites that sustain versus those that do not. The assessment and analysis of implementation costs will be critical for the government as they develop their plan for widespread scale-up.

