Implementation outcomes. For Aim 2, with the focus on implementation process outcomes (rather than client services outcomes), the data are structured with three periods (level-1) within sites (level-2). The outcomes include the proportion of implementation activities completed, duration of activity completion, maximum implementation stage reached, and benchmarks on the Five-80s (3 consecutive months for implementation, 6 consecutive months for sustainment). The model will include key client and site characteristics, and dummy-coded indicators to differentiate the three periods. The results will indicate the difference between Enhanced and Standard in the level of each implementation outcome. As with Aim 1, the conclusions will be validated based on single-level models with fixed-effect control variables for site differences. Likewise, with the focus on achieving implementation process benchmarks, the model

will be extended to a time-to-event framework,²⁹ testing for differences between Enhanced and Standard in the time required to achieve benchmarks (adjusted for the duration of the Standard period). With the focus on implementation process outcomes, power for this aim is inherently limited. Results will focus on estimates of 95% CIs for the effect of Enhanced Implementation.

Attrition & Missing Data. Following intention-to-treat principles, sites will be retained in research measurement independently of participation in Enhanced Implementation.³⁴ Highly successful tracking and retention protocols will minimize missing data. However, some data will inevitably be missing. To address this, assumptions will be evaluated, and informed by the results, one of several approaches will be used³⁵: i) For a small proportion of missing data with evidence of Missing at Random (MAR), the data will be analyzed using the estimation procedures described above. ii) For a non-trivial amount of missing data and evidence of MAR, multiple imputation for repeated measurements will be used.³⁶ iii) For a non-random missing data mechanism, pattern mixture models will be used to identify and control the effect of the non-random mechanism.^{37, 38}

Data Analysis

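### The Aim 2 cost model predicts sustainment for one year after SIC Stage 8, not the six continuous months of the Five-80s that the plan uses as its definition everywhere else

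*Combined protocol and SAP*

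**What the plan says.** Under Research Aims & Abstracts the plan states: "Sustainment will be defined as achieving the Five-80s continuously over 6-months". Study Design repeats this ("Sustainment will be defined as achieving the Five-80% targets continuously", again over 6 months). Both sections define successful implementation separately, as the same five targets held for three months in a row. Both also state the hypothesis that "time and resources spent in Pre-Implementation will be associated with higher odds of successful implementation and sustainment".

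In the SAP, the Implementation outcomes paragraph for Aim 2 lists "benchmarks on the Five-80s (3 consecutive months for implementation, 6 consecutive months for sustainment" among its outcomes and compares Enhanced with Standard on them.

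The preceding SAP text, Evaluation of Specific Aim 2, sets up the cost analysis. It says that cost measures will enter "in a model predicting successful implementation". It continues: "The aggregated cost variables will be added to linear probability models", alongside the SIC Duration and Proportion scores. The binary outcome of those models is "whether a program sustained a minimum of 1-year post Stage 8 of the SIC (Competency". It then plans to compare resource use between sites that sustain and sites that do not, without saying which definition sorts them.

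**The concern.** Sustainment is one of the two results that the time-and-resources hypothesis is about. If the model that could address it classifies sites by another event, its coefficients do not answer the question posed. A reader of the results could also meet two sets of sustained sites under one name. The SAP describes the cost work as critical to the government's scale-up planning, so the label matters to the people who will use it.

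There is a further question. A one-year outcome needs a year of observation after Stage 8, and the plan gives no rule for a site that has less, or for a site that never reaches Stage 8.

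**Working it through.** There is no sample size or power figure to reproduce here. The check is a comparison of definitions, followed by calendar arithmetic.

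**Definitions side by side**

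| Feature | Research Aims, Study Design and Implementation outcomes | Cost model (Evaluation of Specific Aim 2) |
|---|---|---|
| Duration | 6 months | at least 12 months |
| Start of clock | any unbroken run | after SIC Stage 8 |
| Criterion | all five 80% targets | not defined |
| Label | sustainment | sustained, in a model introduced as one of successful implementation (elsewhere 3 months of the targets) |

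The required duration is 12/6 = 2 times as long. Take the reading most favourable to the plan, in which sustained means the five targets held throughout the year after Stage 8. Every site that passes the cost-model outcome then passes the six-month one, but not the reverse: a site that holds the targets for 6 months but not for the full year is sustained in one analysis and not in the other. If sustained means only that the program is still running, neither outcome implies the other.

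**Which analysis addresses which hypothesis.** The Implementation outcomes model uses the six-month benchmark, but its contrast is Enhanced versus Standard. Its time-to-event extension makes the same contrast. The model with cost and SIC Duration as predictors is the cost model, and no other regression described relates those predictors to sustainment.

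**Follow-up after Stage 8.** Inputs: pre-baseline of 6 months and Experiment Period of 12 months (Study Procedures); first Baseline of 6 months, then blocks of 2 of the 8 sites at six-month increments, hence 4 blocks (Study Design). Counting months from the start of pre-baseline:

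- Experiment start = 6 + Baseline, with Baseline 6, 12, 18, 24: months 12, 18, 24, 30.
- Experiment end = start + 12: months 24, 30, 36, 42.

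The length of the Post-Experiment-Sustainment Period is not stated. Assume a common end of follow-up T. Time after the Experiment Period is T minus its end, and a full year after Stage 8 is observable only if Stage 8 is reached by month T − 12.

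| T (assumed) | Post-experiment months, blocks 1–4 | Latest Stage 8 month |
|---|---|---|
| 48 | 24, 18, 12, 6 | 36 |
| 54 | 30, 24, 18, 12 | 42 |
| 60 | 36, 30, 24, 18 | 48 |

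At T = 48 the limit for block 4 is 36 − 30 = month 6 of its Experiment Period. At T = 54 it is 42 − 30 = month 12, the end of that period. Six post-experiment months are available to every block at T = 48 or later.

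If instead every site has the same post-experiment length of P months, a site reaching Stage 8 after month P of its Experiment Period lacks the full year, whichever block it is in.

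**The case against.** The best defence is that the two Aim 2 models ask different questions, one about the effect of the period and one about cost predictors, and that a one-year horizon from Stage 8 can be a legitimate SIC measure. The cost-model text never says that it tests the Pre-Implementation hypothesis. It enters aggregated costs, so changing the outcome alone would not isolate Pre-Implementation resources. The criterion is undefined rather than shown to be different, and it might still be the five targets. All of this is fair. It narrows the point but does not remove it: nothing marks the one-year measure as a separate outcome, and the hypothesis on time and resources is left without a model on its own definition.

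Three stronger readings are tempting, and the documents do not support them.

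- *Sites with short follow-up will be scored as failures.* No text says so. The Attrition & Missing Data paragraph keeps sites in measurement and offers general methods, though none is tied to this outcome. The linear probability model has no stated censoring mechanism, so the gap is real, but failure scoring is conjecture.
- *The outcome is tied to the randomised sequence.* That needs a common end of follow-up before about month 54 and Stage 8 reached late. With an equal post-experiment period per site, block plays no part.
- *With a short post-experiment period, only sites reaching Stage 8 early in Enhanced could qualify.* SIC is also applied as an assessment tool during Standard, and nothing rules out Stage 8 being reached then. Block 4 has 24 months of Standard against 6 for block 1, so even the direction of a sequence effect is not established.

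**Conclusion.** The inconsistency is explicit in the current text, and it lies within the SAP's own Aim 2 material as well as between the SAP and the hypotheses. The cost-model outcome differs in duration (12 against 6 months) and in start point, and its criterion is undefined. The hypothesis linking time and resources to sustainment is therefore not tested on the plan's own definition. That part rests on no assumption.

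The follow-up point is secondary and conditional. With a common end at month 48, a block-4 site reaching Stage 8 after month 6 of Enhanced lacks a full year of observation. At month 54 or later, no site reaching Stage 8 by the end of its Experiment Period is affected. Block 4 holds 2 of the 8 sites, so if both were affected and were counted as failures (which the plan does not say), the observed proportion could fall by up to 2/8 = 25 percentage points.

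The scope is the Aim 2 cost analysis. Aim 1 and the Enhanced-versus-Standard comparison of sustainment stand as written.

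**What to change.** In Evaluation of Specific Aim 2, make the five targets met for 6 consecutive months the outcome of the cost model, and use the same definition to sort sites in the resource comparison that follows. Correct the sentence that introduces the model as one of successful implementation, or state that a second model on the three-month benchmark is intended. If the model is meant to test the Pre-Implementation hypothesis, say so and name the Pre-Implementation cost and duration terms.

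If the one-year measure is kept, label it a separate secondary outcome and define sustained. Treat sites with less than a year observed after Stage 8 as censored or not evaluable rather than as failures, and give a rule for sites that never reach Stage 8. State the length of the Post-Experiment-Sustainment Period and whether follow-up ends on a common date.

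The cost is a few sentences in the SAP. The six-month benchmark is already a planned outcome, so no new data are needed.

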All data will be in electronic format and we will not have any hard copy of study data. In general, we will use Secure Sockets Layer (SSL) encryption to securely transfer the study data that are in electronic format. We will store study data on password-protected, encrypted computers, and will restrict access to the data to key study personnel.

This study will analyze data from five different sources. Here is a detailed description of how we will ensure confidentiality and safely stored data from five different sources:

1. SIC and COINS data

Description: The PrEP-SIC data includes a log of implementation activities completed by each site along with the dates of activity completion (e.g.: date written PrEP implementation plan completed, date first PrEP user retained in care for six months). The COINS tool assesses direct and indirect expenses, including the number of hours per role expected in completing each implementation activity listed in the SIC. SIC and COINS data will be collected by our Yunnan-based research coordinator through phone call and in-person site visits at two to four-week intervals and entered

into the SIC website. SIC and COINS tool measures implementation process and does NOT contain personal identifiable information (PII) or protected health information (PHI).

2. PrEP M&E data

Description: Yunnan CDC (our primary collaborator in China and a subaward recipient on this grant) is upgrading their HIV prevention monitoring and evaluation (M&E) system to incorporate PrEP service delivery indicators. We expect this PrEP M&E data system to start working in May 2020, and it will document data including routine HIV utilization, PrEP service delivery and process measures for all facilities involved in PrEP implementation across the province and including at our study site. Yunnan CDC staff will extract data and aggregated at site level (e.g. number of HIV testing done per site, percentage of MSM clients receiving sexual health needs assessment, number of PrEP initiations). Only this site-level, aggregated data will be shared with the B-HAPPY study team.

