Traditional designs—whether client-randomized or site-randomized—were not viable due to statistical power, contamination risk, and the dual focus on intervention and implementation outcomes. For instance, randomizing clients would risk contamination within sites, and randomizing sites would drastically restrict power. This

is addressed by the proposed stepped-wedge design,²⁵⁻²⁷ with all sites participating in a baseline period (Standard Implementation), experiment period (Enhanced Implementation), and post-experiment period (Observation). Blocks of sites are randomized to the *timing* of the experiment period. Because intervention condition *changes over time*, the intervention effects reflect within-block changes (e.g., between the Enhanced and Standard periods). The design is highly flexible and maximizes power, and the proposed analyses straightforwardly accommodate different data structures for client-services outcomes (Aim 1) and implementation process outcomes (Aim 2), clients that span periods, and outcomes that are both research- and site-collected.

Data structure. For Aim 1, the *client-services outcomes* are structured with repeated visits (level-1) that are nested within clients (level-2) who are nested within periods (level-3) that are nested within sites (level-4). However, for analysis, the outcomes will reflect a single status for each client (e.g., initiation of PrEP), reducing the data to a three-level structure. For Aim 2, the *implementation process outcomes* are structured with three repeated measurements (i.e., across the baseline, enhanced, and observation periods; level-1) that are nested within sites (level-2). In each case, the small number of sites will be addressed. Of note, across aims, supplementary time-to-event analyses^{28, 29} (e.g., the effect of Standard Implementation on time to client awareness) are possible by reformulating the data to client- and site-period structures. Likewise, clients will be associated with the period in which the outcome status is finalized.

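### Aim 2 compares SIC proportion completed and maximum stage by period without a calendar-time term or scoring rule, so with no Enhanced effect the contrast can be far from zero in either direction

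*Combined protocol and SAP*

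**What the plan says.** - **The outcomes.** The SAP, Implementation outcomes, lists them for Aim 2: "The outcomes include the proportion of implementation activities completed, duration of activity completion, maximum implementation stage reached", followed by the Five-80 benchmarks.
- **The data.** Under Confidentiality of study data, item 1 (SIC and COINS data), the SIC record is described as "a log of implementation activities completed by each site along with the dates of activity completion". One example item is the "date first PrEP user retained in care for six months", an event that a site can have only once.
- **The layout.** In the SAP, Implementation outcomes, "the data are structured with three periods (level-1) within sites (level-2"). With eight sites that is 8 × 3 = 24 records per outcome.
- **The model.** "The model will include key client and site characteristics, and dummy-coded indicators to differentiate the three periods". The result is read as the Enhanced-versus-Standard difference in the level of each outcome. The conclusions are then checked in single-level models with site fixed effects.
- **The order.** Study Design and Study Procedures give a six-month first Standard period, crossover of two sites every six months, and one year of Enhanced, always after Standard.
- **Time control.** Linear and quadratic time terms appear only under Evaluation of Specific Aim 1, for the client-level models. The one timing adjustment in Aim 2 is for the length of Standard, in the time-to-event extension for benchmarks.
- **Role of the SIC.** In Standard the SIC only observes. Study Design distinguishes Enhanced, "when it will be used both to guide implementation and to assess it".

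No section says whether proportion completed and maximum stage are scored cumulatively, as new completions in the period, or by starting the list again.

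**The concern.** A dated completion log accumulates with time. When every site passes through the periods in the same order, a period indicator with no time term picks up elapsed time along with any effect of Enhanced. The direction of the resulting bias depends on a scoring rule that the SAP does not give. Carrying scores forward favours Enhanced, because a running total or running maximum cannot fall. Counting only new completions usually disfavours it, because fewer activities remain open, and the shortfall grows with the randomised length of Standard.

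At stake is whether two of the named Aim 2 process outcomes can be read as evidence about Enhanced. Two analysts following the same SAP could report conclusions of opposite sign from the same log.

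**Working it through.** The documents give no effect size, power or expected value for these outcomes, so there is no planned figure to reproduce.

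**Inputs from the documents.** Eight sites in four blocks of two. Standard lasts 6 + 6k months for k = 0 to 3, that is 6, 12, 18 or 24 months (derived from Study Design). Enhanced lasts 12 months (Study Procedures).

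**Assumptions, not in the documents.** Enhanced has no effect. Each activity has a constant completion rate with median m months, m from 6 to 24. The proportion complete at time t is then P(t) = 1 - 2^(-t/m).

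In a balanced model with site and period indicators, the Enhanced coefficient is the mean within-site difference. For a site with Standard length s:

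- cumulative scoring: P(s+12) - P(s)
- new completions only: [P(s+12) - P(s)] - P(s)
- restart in each period: P(12) - P(s)

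**Worked case, m = 12.**

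| Standard (months) | 6 | 12 | 18 | 24 | Mean |
|---|---|---|---|---|---|
| End of Standard, % | 29.3 | 50.0 | 64.6 | 75.0 | 54.7 |
| End of Enhanced, % | 64.6 | 75.0 | 82.3 | 87.5 | 77.4 |
| Cumulative difference | +35.4 | +25.0 | +17.7 | +12.5 | +22.6 |
| New-only difference | +6.1 | -25.0 | -47.0 | -62.5 | -32.1 |

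On restart, P(12) = 50.0%, so the mean difference is 50.0 - 54.7 = -4.7 points.

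**Mean null difference by median, in points (calculated before rounding).**

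| m (months) | Cumulative | New only | Restart |
|---|---|---|---|
| 6 | +17.6 | -59.0 | -1.6 |
| 9 | +21.6 | -42.5 | -3.8 |
| 12 | +22.6 | -32.1 | -4.7 |
| 18 | +21.5 | -20.5 | -5.0 |
| 24 | +19.4 | -14.6 | -4.6 |

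**Simulation of the SAP's fixed-effects check.** 2000 null trials per rate were fitted by least squares to 24 records with site and period indicators. Assumptions: 40 activities, monthly completion rates of 0.02, 0.04 and 0.08, log-normal site variation (SD 0.3) and a 12-month post-experiment period.

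- Cumulative: p < 0.05 in favour of Enhanced in 100% of trials at all three rates.
- New only: p < 0.05 against Enhanced in 38%, 89% and 100%.
- Restart: p < 0.05 in about 6%, 3% and 1%.
- Maximum stage under cumulative scoring was never lower in Enhanced than in Standard.

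**Does using the randomised timing remove the bias?** The same null process, with cumulative scores in six-month calendar steps, site and calendar-step indicators and a time-varying Enhanced indicator, gave mean Enhanced coefficients of 0.001, 0.000 and 0.000 (simulation standard error about 0.0007). Modelling the completion rate among open activities with the same terms (medians 6, 12 and 24; 150 trials per setting) gave a mean log rate ratio of 0.008 to 0.019 with no effect (simulation standard error 0.02 to 0.03). It gave 0.66 to 0.69 when the true value was 0.693, a doubling of the rate.

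**The case against.** The strongest reply is that the SIC may be worked through afresh in Enhanced. Study Design has sites follow its eight stages during that period, and "three repeated measurements (i.e., across the baseline, enhanced, and observation periods; level-1") fits three separate passes. This stands as a possible reading: it is not stated, and a once-only item such as the first retained user fits it poorly, but nothing excludes it. Under it the distortion is small and comes from unequal period lengths. A reader might infer that SIC items are never reversed and that the contrast is therefore fixed by scoring alone; the documents support the first only as an inference, and so do not establish the second.

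A reader might also conclude that the result would be the same whatever Enhanced does. It would not. Under cumulative scoring the sign is constrained, but the size still responds to Enhanced. Under new-only scoring with m = 24, mean Standard completion is 33.9%; if Enhanced completed everything left, the difference would be 1 - 2 × 0.339 = +32 points. With m = 12 the 6-month block shows a gain even under no effect. The contrast is biased, not empty. Nor is the bias beyond repair by a time term: calendar-step terms remove it from cumulative scores.

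Two planned features might seem to cover the gap. The time-to-event extension addresses benchmarks, and other time-to-event analyses are described only as supplementary and possible; neither replaces the level contrast. The SAP concedes limited power and focuses on 95% intervals, but an interval centred on a biased value does not address bias.

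Other extensions are unsupported. No bias has been shown for duration of activity completion. A sign test on eight increases would be off-plan, and ties are possible. No section makes the implementation blueprint depend on this contrast alone.

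**Conclusion.** The concern holds for proportion of activities completed and maximum stage reached. The listed model has no calendar-time term and no scoring rule. Under cumulative or new-only scoring it gives a materially biased contrast: with no effect, proportion completed differs on average by about +18 to +23 or -15 to -59 points. Under a restart the bias is about -2 to -5 points. These sizes rest on assumed constant completion rates with medians of 6 to 24 months and on Standard lengths of 6, 12, 18 and 24 months. That a cumulative score or running maximum cannot fall does not depend on those rates. Size was not calculated for maximum stage. The Five-80 benchmarks can reverse and fall outside this point.

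**What to change.** 1. State in the SAP how SIC items are scored in each period: cumulative, new completions only, or restarted.
2. For proportion completed and maximum stage, replace the period-indicator contrast with one that uses the randomised timing. Either (a) analyse cumulative scores by calendar step, with site and calendar-time terms and a time-varying Enhanced indicator; or (b) analyse the completion rate among still-open activities from the logged dates, with the same terms. If sites do restart the SIC, define the open set for each pass, so that the Enhanced pass is not discarded.
3. For duration, state how an activity that spans two periods is assigned.
4. Note in the interpretation that, because the SIC guides Enhanced, SIC completion partly reflects delivery of the strategy.

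Cost: SAP wording and some re-programming. No new data are needed, since SIC data are already collected at two- to four-week intervals. Intervals will be wider, and under (b) activities closed during Standard carry no information about Enhanced.
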